25.2 Retention of blood samples

Storage and disposition of blood samples analysed at local laboratories will be performed according to local laboratory procedures.

Remaining blood not used for the primary analysis mentioned in this protocol will be stored for future exploratory analysis until the trial has been evaluated by appropriate authorities or the project terminates or until the exploratory analysis has been performed, but no longer than 15 years from the end of the trial. As new biomarkers related to the disease and/or safety, efficacy, or mechanism of action of turoctocog alfa may evolve during the conduct of the trial, the analyses of the stored blood samples may also include biomarkers that are unknown at present or have not been included in the scientific hypotheses at initiation of the trial.

Parents will be requested to consent to the long-time retention and exploratory analysis of blood samples, see section 19.1

The samples will be stored at Novo Nordisk or a Novo Nordisk designated referral bio-repository with access to the samples. Samples might be transferred to other countries, if not prohibited by local regulations. The patient's identity will remain confidential and samples will only be marked and identified by a unique sample ID. No direct identification of the patient will be stored together with the samples. The analyses will not have any medical consequences for the patients or their relatives. Only Novo Nordisk staff and bio-repository personnel (if applicable) will have access to the stored bio specimens.

In the event that the collected blood samples will be used in the future, the investigator will become directly informed by Novo Nordisk about the results if the findings are deemed clinically and analytically valid and quantifiable. In such case, a written summary of the findings, including listings of subject specific values, will be provided once a firm conclusion from the results has been drawn by Novo Nordisk. Potentially, observations of neoplastic diseases, serious genetically

hereditary diseases, other un-treatable diseases, or any other abnormal findings could be part of the observations. Subjects may at any time contact the investigator if they wish to be informed about results derived from stored blood samples obtained from their own body.

Subject information/Informed consent

1 Information about the trial and the trial product

1.1 Overview of changes

1. Deleted appendix A (Table of contents)
2. Added items in list of abbreviations. (List of abbreviations)
3. Deleted sentence in the Summary stating that initial infusions of trial product should be done at investigational site. (Summary)
4. Clarified and corrected footnotes in visit flow charts. (Section 2)
5. Clarified in the visit flow chart for the extension trial phase that genotype can be tested at unscheduled visits. (Section 2)
6. Added visit flow chart table describing which assessments to be done at the unscheduled visit for inhibitor confirmation, and at the inhibitor unscheduled visit(s). (Section 2)
7. Clarified that eligible patients can receive first dose at Visit 2. (Section 5.1)
8. Changed the maximum duration of treatment of a patient from first to last turoctocog alfa administration. (Section 5.3)
9. Clarified how patients can be treated with turoctocog alfa. (Sections 5.3 and 9.5)
10. Clarified in section 5.3.2 that all treatments administered in relation to bleeds must be recorded as 'treatment of bleeds'.
11. Updated trial timelines. (Section 7)
12. Clarified that the main purpose of Visit 2 is to enrol eligible patients, to dispense the trial product and to administer turoctocog alfa for the first time, if applicable. (Section 8.1.3)
13. Added that patients with inhibitors must attend inhibitor unscheduled visit at least every third month. (Section 8.1.5.2)
14. Clarified in the list of assessments to be performed at inhibitor unscheduled visit, that Lupus anticoagulant and FVIII Non-neutralising antibodies should be performed. (Section 8.1.5.2)

15. Clarified that the minimum 48 hours washout period of turoctocog alfa does not apply for inhibitor patients on ITI treatment. (Section 8.2.2.1)
16. Added that 'used' vials should be recorded in the IV/WRS Drug Accountability module. (Section 9.4)
17. Added that treatment with blood and blood component products containing FVIII, e.g. cryoprecipitate and plasma except during surgery should be avoided during the course of the trial. (Section 11)
18. Deleted MESI reporting timelines in section 12.1.2 Medical Event of Special Interest and other events for expedited reporting. (Section 12.1.2)
19. Changed minor inconsistencies, ambiguities and typographical errors.

Subject information/Informed consent:

No changes to the Subject information/Informed consent.

1.2 Rational for changes

1. Appendix is not required to be included in the protocol and has therefore been deleted.
2. Description of two abbreviations were missing.
3. The sentence was inserted in error and the deletion is in accordance with the Protocol.
4. To ensure alignment with the Methods and Assessments section of the Protocol.
5. To ensure alignment with the Methods and Assessments section of the Protocol.
6. To make it clear how to conduct Unscheduled Visit with inhibitor confirmation and Inhibitor Unscheduled Visit.
7. To make it clear that patients will not necessarily be administered the first dose at Visit 2. The first dose may be administered at a later time point.
8. To reflect the expected maximum treatment duration.
9. To clarify that patients can be treated at non-investigational site in addition to treatment at investigational site and at home. Furthermore the section describing that investigator needs

to instruct patients/parents/caregivers/support persons in how to handle administration of turoctocog alfa has been moved from Section 9.5 Trial Product Administration to Section 5.3 Treatment of Patients.

10. To ensure that all treatments of turoctocog alfa administered in relation to bleeds are reported as 'treatment of bleeds'. This ensures consistent reporting of the treatment of bleeds.
11. Timelines have been revised to reflect an extension of the recruitment period.
12. To detail that the main purpose of Visit 2 is to enrol eligible patients and to dispense trial product in addition to administer trial product for the first time, if applicable.
13. To ensure that patients with inhibitors attends inhibitor unscheduled visits with a frequency that allows close follow up on safety and efficacy status and on the inhibitor status.
14. To clarify that Lupus anticoagulant and FVIII non-neutralising antibodies should be performed at inhibitor unscheduled visit. This is in accordance with the visit flow chart and with the description of the two assessments Lupus anticoagulant and FVIII non-neutralising antibodies.
15. The 48 hours washout period is not applicable for patients on ITI treatment, where the treatment regimen require daily administration of turoctocog alfa.
16. All vials; used, unused and lost should be recorded in the IV/WRS Drug Accountability module. The word 'used' was by error deleted in the former version of the protocol.
17. To avoid the use of blood and blood component products containing FVIII as these treatments may confound the effects of the investigational product.
18. MESI reporting timelines were not correctly defined in section 12.1.2. The correct MESI reporting timelines are defined in section 12.2 Collection, Recording and Reporting of Adverse Events.
19. To enhance the quality of the Protocol.

Subject information/Informed consent:

Not applicable.

In this protocol amendment:

- Any new text is written *in italics*.
- Any text deleted from the protocol is written using ~~strike through~~.

2 Changes

Table of Contents

...

Appendix E

**Patient Reported Outcome Questionnaire, Version 6.0 dated 12 June
2014**

...

List of abbreviations

NB

nota bene (take notice)

PUP

previously untreated patients

1 Summary

...

Trial Product

...

~~The initial infusions will be administered at the investigational site, but after adequate instruction and practice the goal is to implement home treatment with intravenous (i.v.) injections given by the parent or a support person.~~ Turoctocog alfa will be supplied as freeze dried powder to be reconstituted with a sterile sodium chloride solution for injection.

2 Flow Chart

Table 2-1 Visit Flow Chart main trial phase

Visit number	Screen. Visit 1	Visit 2 [#]	Visit 3	Visit 4	Visit 5	Unscheduled Visit
Visit window	NA	≤ 21 d post V1	10 th -15 th ED	20 th -25 th ED	50 th -55 th ED	
PATIENT RELATED INFO / ASSESSMENTS						
Informed consent	●					
Inclusion/Exclusion Criteria	●	●				
Consent for genotype test	●b					
Biospecimen consent	●b					
Withdrawal Criteria		●	●	●	●	●b
Haemophilia treatment history	●					
Concomitant illnesses / Medical history	●					
Concomitant medication	●	●	●	●	●	●b
Demography	●					
Body measurements	●	●d	●d	●d	●	●b,a,d
Genotype test ⁴			●b,f	●b,f		●b,f
Details of haemophilia	●					
EFFICACY						
Bleed(s)		●	●	●	●	●b
SAFETY						
Adverse events	●	●	●	●	●	●b
Physical examination	●	●	●	●	●	●b,a
Vital signs	●				●	
FVIII activity	●ac					
Antibodies - FVIII inhibitors - FVIII non-neutralising antibodies	●ac		●ac	●ac	●ac	●a, c,b
Lupus Anticoagulant						●b
FVIII trough level			●ab	●ab	●ab	●ab
FVIII recovery		●ab	●ab	●ab	●ab	●a b,e
Biochemistry	●				●	●a
Haematology	●				●	●a
OTHER ASSESSMENTS						
PRO questionnaire			●		●	
HE assessment		●b	●b	●b	●b	●b
Viral antibody test	●i					●ab

Visit number	Screen. Visit 1	Visit 2 [#]	Visit 3	Visit 4	Visit 5	Unscheduled Visit
Visit window	NA	≤ 21 d post V1	10 th -15 th ED	20 th -25 th ED	50 th -55 th ED	
T cells subset: CD4+	•b, h	•b, h				•b, h
TRIAL MATERIAL						
turoctocog alfa administration		•ab	•a-b	•a-b	•ab	•ab
Home treatment training		•				
Diary and/or Trial card dispensing and/or collection ^e	•e	•e	•e	•e	•e	•b, e
Review of patient diary and entry of data in eCRF			•	•	•	•b
Enrolment session in IV/WRS	•					
Drug dispensing and accountability		•g	•	•	•	•b
Diary training		•				

- Visit 2 can be performed at the same day as Visit 1

a – minimum 48 hours washout period of turoctocog alfa (or blood component products at Visit 1).

a – optional, at discretion of Investigator

b – if applicable ~~or optional~~

c – mandatory to confirm clinical relevant inhibitors~~c~~

c – Minimum 48 hours washout period of turoctocog alfa (or blood component products at Visit 1). Not a requirement for patients on ITI treatment.

d – weight only

e – Visit 1 trial card only, Visit 2-5 diary only

f – if previous tests are not available, if allowed by local law and after consent

g – Visit 2 dispensing only

h – if HIV positive, last value of CD4+ T-cells (if available), or new cell count

i – if HIV, HBsAg and/or HCV status unknown

Table 2-2 presents the rolling visit schedule in the extension phase over the period of one year. It comes to effect after Visit 5 or after inhibitor treatment.

Table 2-2 Visit Flow Chart trial extension phase

Visit type	Dispensing		Assessment & Dispensing	Dispensing		Assessment & Dispensing	End of Trial	Unsch Visit
Visit number[#]	6 7		8	9 10		11		
Previous visit time(w)	-8	-8	-10	-8	-8	-10	< 8	
Visit window	± 1w	± 1w	± 1w	± 1w	± 1w	± 1w	NA	NA
ASSESSMENTS								
Withdrawal Criteria	●	●	●	●	●	●		●b
Concomitant medication	●	●	●	●	●	●	●	●b
Body measurements			●c			●c	●	●a, c
Genotype								●b
EFFICACY								
Bleed(s)	●b	●b	●b	●b	●b	●b	●b	●b
SAFETY								
Adverse events	●	●	●	●	●	●	●	●b
Physical examination			●a			●a	●	
Vital signs			●a			●a	●	
Antibodies ^f - FVIII inhibitors - FVIII non-neutralising antibodies	●a, f	●a, f	●, f	●a, f	●a, f	●, f	●, f	●a, f
Lupus Anticoagulant								●b
FVIII trough level	●a	●a	●a	●a	●a	●a		●a
FVIII recovery	●a	●a	●a	●a	●a	●a		●a
Biochemistry			●			●	●	●a
Haematology			●			●	●	●a
OTHER ASSESSMENTS								
PRO questionnaire						●	●	
HE assessment	●b	●b	●b	●b	●b	●b	●b	●b
Viral antibody test							●	●a
T cells subset: CD4+							●	●b
TRIAL MATERIAL								
turoctocog alfa administration	●a	●a	●a	●a	●a	●a		●a
Diary dispensing and/or collection	●	●	●	●	●	●	●d	●b
Review of patient diary and entry of data in eCRF	●	●	●	●	●	●	●	●b
Completion session in IV/WRS							●	
Drug dispensing and accountability	●	●	●	●	●	●	●e	●b
EoT form							●	

- Presented numbers are for the first 12 months. Visit numbers for future years will be in consecutive order

a – optional, at discretion of investigator

b – if applicable

c – weight only

d – collection only

e – accountability only

f - Minimum 48 hours washout period of turoctocog alfa. Not a requirement for patients on ITI treatment.

Table 2-3 presents the assessments to be made at unscheduled visit with inhibitor confirmation and at inhibitor unscheduled visit.

Table 2-3 Visit Flow Chart inhibitor related visits

Visit type	Inhibitor confirmation at Unscheduled Visit	Inhibitor Unscheduled Visit
PATIENT RELATED INFO / ASSESSMENTS		
Withdrawal Criteria		•b
Concomitant medication		•b
Body measurements		•a, c
EFFICACY		
Bleed(s)		•b
SAFETY		
Adverse events		•
Physical examination		•b
Antibodies - FVIII inhibitors - FVIII non-neutralising antibodies	•e	•a, e
Lupus Anticoagulant	•	•d
FVIII trough level	•a	•a
FVIII recovery	•	•a
OTHER ASSESSMENTS		
HE assessment		•b
TRIAL MATERIAL		
turoctocog alfa administration		•a
Diary dispensing and/or collection		•b
Review of patient diary and entry of data in eCRF		•b
Drug dispensing and accountability		•b

a – optional at discretion of investigator

b – if applicable

c – weight only

*d – In the event that a patient has both a positive Lupus Anticoagulant and a positive confirmatory inhibitor test, Lupus Anticoagulant must be taken at every subsequent inhibitor test thereafter until the inhibitor test is negative (<0.6 BU).
e – Minimum 48 hours washout period of turoctocog alfa. Not a requirement for patients on ITI treatment.*

...

5 Trial Design

5.1 Type of Trial

...

The trial consists of two phases i.e. main and extension, respectively. In the main phase the patients will attend a screening visit (Visit 1) in order to assess their eligibility. At Visit 2 eligible patients ~~will can~~ receive their first dose, if applicable.

...

5.3 Treatment of Patients

...

Patients will enter a bleeding preventive regimen as described below, see Section 5.3.1. For prevention one single bolus dose of turoctocog alfa is administered intravenously (i.v.) at each administration day. Turoctocog alfa should preferably be administered in the morning. The maximum duration of treatment of a patient from first to last turoctocog alfa administration is approximately 5–4 years.

...

~~In most cases, treatment will be given at home with i.v. self injection by the parent/caregiver/support person. However, on days when the patient is attending a trial visit, if applicable the dose may be administered at the clinic by a health care professional. Initially treatment with turoctocog alfa will typically be carried out by the staff at the clinic. Treatment can also be given at home with i.v. injection by the parent/caregiver/support person and/or at a non-investigational site. All patients and/or parents/caregivers/support persons will be instructed by Investigator how to handle administration of turoctocog alfa before first dose is administered at home or at non-investigational site.~~

...

5.3.2 Treatment of Bleeds

~~During preventive treatment, break through bleeds may occur and require extra doses of turoctocog alfa.~~ Treatment of bleeds should be started as soon as a bleed is identified. All bleeds, mild/moderate and severe, can be treated at home. For severe bleeds (see Section 8.3.1.1) the Investigator should evaluate if the patient should be seen at the clinic. All bleeds must be reported to the clinic within 24 hours from onset of the bleed.

The dose for treatment of bleeds should aim at providing a post injection level of FVIII *according to Table 5-1 of at least 0.50 IU/mL or 50 IU/dL*.

...

Each administered dose (mL given, vial strength and time of day) as well as efficacy in treatment of bleeds will be registered in the diary and in the eCRF. *All treatments (excluding ITI treatment) administered in relation to bleeds must be recorded as 'treatment of bleeds', e.g. scheduled preventive treatment administered between start and stop time of a bleed must be registered as 'treatment of bleed'.*

...

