8.3 Assessments for Efficacy

8.3.1 Bleeds

During the entire trial period all bleeds treated with N8 will be entered in either the eCRF or in the patient's diary. For mild/moderate bleeds, the patient or caregiver must fill in the diary and at visits the diary data will be transcribed into the eCRF by trial site personnel. For severe bleeds (see definition in Section [\(8.3.1.1\)](#)) the Investigator, or designated site staff, must be contacted without delay to prescribe the appropriate treatment and any follow-up procedures. It is recommended that these direct instructions are followed by, or given at, an unscheduled visit to the clinic.

Documentation about the severe bleed should be entered in the medical records and eCRF by the trial personnel.

All bleeds should be reported to the clinic within 24 hours. However, if there is no haemostatic improvement within 8 h after one dose, immediate contact should be taken with the Investigator/site staff for advice.

Joint bleeds are either categorised as target joint or non-target joint bleeds. Target joint bleeds are defined as 3 or more bleeds in the same joint within 6 months. When there has been no bleed in this same joint for 12 months, such a joint is no longer considered a target joint.²³

For bleeds the following will be recorded in the patient diary:

- Date and time of onset of bleed
- Location of the bleeding (central nervous system (CNS), haemarthrosis (joint), gastrointestinal, subcutaneous, muscle, mucosal or other)
- Classification of bleed (spontaneous, traumatic)
- Haemostatic drug used for treatment (N8 or other drug if haemostasis cannot be achieved, i.e. bleed cannot be controlled with N8)
- Dose(s) and Time(s) of administration
- Other therapy used (compression/other)
- Date and time of stop of bleed
- The bleeds must be categorised as mild/moderate or severe, see Section [8.3.1.1](#).
- Clinical evaluation of the haemostasis (Excellent, Good, Moderate or None), see Section [8.3.1.2](#)

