and/or for patient, who stay in the trial for a longer duration of time). According to the European regulatory guidelines (Directive 2001/20/EC)^{2,19} the recommended blood volume collected from the patient for all tests should not exceed 1% of the whole blood volume at any single time and 3% of whole blood volume in 28 days (see Appendix B). This is in accordance with Where this guideline is not applicable, local guidelines for blood sampling volumes will apply. During visits when multiple samples are taken, blood samples will be aliquoted to meet above mentioned requirements. Instructions will be provided in the Laboratory Manual and in Appendix B.

2.33 8.2.8 Physical Examination

Physical examination should be performed at Visits 1-5 and at EoT (additional examinations can be performed as appropriate) according to practice at the participating clinic including assessments of the following:

2.34 8.2.9 Vital Signs

Vital signs will be assessed at Visit 1 and Visit 5 and at EoT (additional assessments can be performed as needed) and includes:

- Body temperature (assessed by measuring inner ear temperature or using an oral digital thermometer)
- Respiratory rate (resp./min.)
- ~~Pulse: preferably supine~~
- ~~Blood pressure (BP): preferably supine~~

~~BP (systolic and diastolic) and pulse rate will be measured according to local practice at the clinic; preferably after the patient has rested comfortably for at least 3 minutes.~~

Any changes in the vital signs between the two visits which fulfil the criteria of an Adverse Event must be recorded as such, see Section 12.1.

2.35 8.3.1 Bleeds

During the entire trial period all bleeds ~~treated with turoctocog alfa~~ will be entered in either the eCRF or in the patient's diary. For ~~mild/moderate~~ bleeds *treated at home*, the patient or caregiver must fill in the diary and during visits the diary data will be transcribed into the eCRF by trial site personnel. ~~For severe bleeds (see definition in Section (8.3.1.1) the Investigator, or designated site staff, must be contacted without delay to prescribe the appropriate treatment and any follow-up procedures. It is recommended that these direct instructions are followed by, or given at, an unscheduled visit to the clinic. Documentation about the severe bleeds treated at the clinic should be entered in the medical records and eCRF by the trial personnel.~~

2.36 8.4.1 FVIII genotype testing (not applicable to Brazil)

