Severe: Major bleeds that require hospitalisation. All internal head and neck bleeds must be categorised as severe. Muscle bleeds with compartment syndrome and bleeds associated with a significant decrease in the haemoglobin level ($>3\text{g/dl}$) will also be reported as severe and entered in the eCRF. ~~All mild or moderate bleeds which are on-going 24 hours after start will be redefined as severe.~~

2.25 8.3.1.3 Bleed Classification

Re-bleeds will be reported by the trial statistician based on the diary data. Re-bleed is defined as *a bleed* ~~when after an initial period of improvement~~, (worsening of bleeding site conditions e.g. *swelling, pain*) ~~either on treatment or~~ within 72 hours after stopping of *a previous bleed at the same anatomical location*. ~~treatment (therefore, a new bleed is considered occurring later than 72 hours after stopping of treatment)~~

2.26 8.4.1 FVIII Genotype testing

At Visit 1, all patients/parents/legally authorised representative (LAR) will be asked about documentation of previous FVIII and Human Leucocyte Antigen (HLA) genotype tests. If not available or if it needs to be re-tested, *based on the Investigators discretion*, FVIII and HLA genotype testing will be offered as allowed by local law. The blood sample should be taken at Visit 3, 4 or an unscheduled Visit. The FVIII genotype analysis is performed at the laboratory in Bonn, Germany.

Investigator, parent(s) or LAR have the right to refuse to provide patient's FVIII genotype documentation or to refuse genotyping. This will not ~~stop prevent~~ the patient's to continued participation in the remainder of the trial.

Applicable for Japan only: If documentation of the patient's genotype already exists, the patient is offered to provide his data for the trial. If no previous data exists and genotyping consent is obtained, FVIII genotype analysis is performed at the laboratory in Bonn, Germany, using DNA isolated from leucocytes from the patient's blood. No analysis will be performed concerning other genes than FVIII and HLA. Samples will be disposed appropriately after the test and all test results are kept strictly confidential.

2.27 9.1 Trial Products

Novo Nordisk will not supply any non-investigational products (NIMPs).

2.28 9.4 Dispensed and Drug Accountability of Trial Products

Once a patient is dosed, *the allvials (used, partially used, unused, returned, and lost/damaged) must be recorded in the IV/WRS Drug Accountability module.*

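### Section 5.3.2 allows home treatment of severe bleeds, including internal head and neck bleeds, with a 24-hour report as its only contact deadline; the prompt-contact rule in 8.3.1 was probably deleted

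*Combined protocol and SAP*

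**What the plan says.** Section 5.3.2 in the last displayed amendment gives three rules, none of them struck:

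- Place of treatment: "All bleeds, mild/moderate and severe, can be treated at home".
- Investigator's role: "For severe bleeds (see Section 8.3.1.1) the Investigator should evaluate if the patient should be seen at the clinic".
- Reporting: "All bleeds must be reported to the clinic within 24 hours from onset of the bleed".

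Section 8.3.1.1, as amended by Amendment 7 (item 2.24), defines the category: "Severe: Major bleeds that require hospitalisation. All internal head and neck bleeds must be categorised as severe".

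Section 8.3.1 of protocol version 1.0 set two further contact rules beside a 24-hour report. For a severe bleed, "the Investigator, or designated site staff, must be contacted without delay to prescribe the appropriate treatment and any follow-up procedures". For any bleed, "if there is no haemostatic improvement within 8 h after one dose, immediate contact should be taken with the Investigator/site staff for advice". No displayed amendment changes the second rule. The amendment that introduced the main and extension phases displays the first as struck (item 2.35).

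**The concern.** Section 5.3.2 depends on decisions by the Investigator: the dose, the number and frequency of doses, and whether the child is seen. None of these can be made for a particular bleed until the site knows about it. Yet the section that grants home treatment sets the same reporting limit for a mucosal bleed as for an internal head bleed.

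Read on its own, it is satisfied by a caregiver who infuses at home, sees apparent improvement and reports up to 24 hours after onset. Some of these children may not yet be on prophylaxis, since preventive treatment can be deferred until 24 months of age or two bleeds needing treatment (5.3.1). What is at stake is the safety of the individual child; no effect on the primary endpoint or its analysis is claimed.

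**Working it through.** The plan gives no figure to reproduce, so the check is mainly a comparison of versions.

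**1. The text across versions**

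| Point | Version 1.0 | Amendment introducing the two phases | Last displayed text |
|---|---|---|---|
| Home treatment (5.3.2) | Mild/moderate bleeds; severe-bleed treatment to start at home where possible | All severities | All severities |
| Investigator and severe bleeds (5.3.2) | Evaluation mandatory, preferably at the clinic | Evaluates whether the child should be seen | Same; no time given |
| Report (5.3.2) | 24 h from onset, all bleeds | Unchanged | Unchanged |
| Immediate contact for severe bleeds (8.3.1) | Required | Displayed as struck | Not restored in any displayed amendment |
| Contact if no improvement 8 h after a dose (8.3.1) | Required | Not displayed as changed | Not displayed as changed |

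**2. Was the immediate-contact rule deleted?**

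For deletion:
- The same 8.3.1 paragraph replaces the split by severity with a split between bleeds treated at home and bleeds treated at the clinic.
- The same amendment loosens 5.3.2.
- One of its stated aims is an optional phone visit for severe bleeds.

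Against certainty:
- The struck run ends with "Documentation about the severe bleeds treated at the clinic should be entered in the medical records and eCRF by the trial personnel", where the reference to clinic treatment is new wording absent from version 1.0. The strike mark therefore runs over inserted text.
- The struck run in item 2.9 of that amendment covers the Investigator-evaluation sentence that is live in the last displayed 5.3.2.

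Probable deletion is as far as the file supports.

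**3. What follows on each reading**

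- *Deleted:* the 8-hour rule applies only after a dose has been given and only without improvement. A severe bleed that seems to improve triggers nothing before the 24-hour report.
- *Survived:* there is no conflict. Version 1.0 of 8.3.1 held the immediate-contact rule together with "All bleeds should be reported to the clinic within 24 hours", so 24 hours is an outer limit. Section 5.3.2 then only needs to repeat the rule.

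**4. Repeat doses due before the reporting limit**

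Inputs: the repeat interval *i* is 8 to 24 h (Table 5-1, life-threatening haemorrhage). The reporting limit is 24 h from onset (5.3.2). The time *t* from onset to first dose is not given; 0 to 4 h is assumed.

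Repeat doses fall at *t* + *k·i*, for *k* = 1, 2, …; count those strictly before hour 24.

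| *i* (h) | *t* = 0 | *t* = 4 | Doses before hour 24 |
|---|---|---|---|
| 8 | 8, 16 | 12, 20 | 2 |
| 12 | 12 | 16 | 1 |
| 24 | none (24) | none (28) | 0 |

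The range is 0 to 2.

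**The case against.** The strongest objection is that deletion rests on extracted strike marks that demonstrably overrun, and no consolidated 8.3.1 is available. That stands, and it is why the claim stops at probable deletion. The amendment's stated aim explains making the visit optional, but gives no reason to drop prompt contact.

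Second, version 1.0 also kept only the 24-hour limit in 5.3.2 and placed prompt contact in 8.3.1, so a missing shorter limit in 5.3.2 is not in itself a defect. That is fair if 8.3.1 still carries the rule. It does not help if the rule is gone.

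Third, the gap is narrow. Severe bleeds are largely defined by a need for hospitalisation, Investigator evaluation implies contact, home treatment is permissive and early factor is desirable. All true. But the evaluation sentence sets no time, and head and neck bleeds are severe by site, whatever their apparent course.

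Fourth, caregiver training and information may already say when to call. The training content is not in the file and the consent pages were removed, so this cannot be judged either way.

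Fifth, the dose count includes zero, assumes a first-dose time, and uses a table row that the protocol does not equate with its severe category. Table 5-1 is guidance; departing from it is not a deviation, and a dosing plan prescribed in advance could cover some doses. The count therefore shows only that dosing decisions can fall due before the limit.

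**Conclusion.** The concern holds and should be fixed, with medium confidence. The live 5.3.2 covers severe bleeds, including all internal head and neck bleeds, and gives no contact time shorter than 24 hours. If the 8.3.1 rule was deleted, as is probable, a severe bleed that appears to improve after a home dose has no prompt-contact rule anywhere in the displayed protocol. If it survived, what remains is a missing repetition in 5.3.2.

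The size is 0 to 2 repeat-dose decisions per life-threatening bleed before the reporting limit, conditional on the Table 5-1 intervals and the assumed 0 to 4 hours to first dose. No harm figure or patient count can be given, because the documents state no expected number of severe bleeds.

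**What to change.** Confirm the consolidated 8.3.1. Then put a rule to this effect in 5.3.2 and 8.3.1, restoring it in the latter if it was deleted:

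> For any suspected severe bleed as defined in 8.3.1.1, including any suspected internal head or neck bleed, treatment can be started at home, but the Investigator or site staff must be contacted immediately (phone is acceptable) to direct dosing and decide on a clinic visit or admission.

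Keep 24 hours as the outer reporting limit for other bleeds, and keep the 8-hour non-response rule for all bleeds.

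The cost is a few sentences at the next amendment, matching caregiver instructions, and some earlier calls to sites. No visit or procedure is added: the trial card already carries the clinic's telephone numbers (8.1.2), dosing can already be prescribed by telephone (5.3.2), and the optional phone visit stays.
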